Cover page

Official title: 8.4% Sodium Bicarbonate Locks in Intestinal Failure

NCT number: NCT05813535

Document date: 10/2/2025

Study Protocol and Statistical Analysis Plan

Study design

This was an open-label prospective cohort study on pediatric patients with IF followed by the Pediatric Intestinal Rehabilitation program at a tertiary medical center assessing the rates of CRBSI and CVC replacement. The study was approved by the institutional review board.

Consent was obtained from caregivers. This trial was registered on Clinicaltrial.gov (NCT05813535). The study covered a period between January 1, 2021, and March 1, 2025. Baseline (preintervention) period covered January 1, 2021, until start of NaHCO₃ locks while patients were on heparin locks. The intervention period covered the start of NaHCO₃ lock use until the end of the study period or until discontinuation of NaHCO₃ locks, whichever occurred earlier. Data from baseline period (while on heparin locks) were reviewed retrospectively. In our practice, we primarily use a single lumen silicone CVC for PN delivery for patients with IF but may use a polyurethane peripherally inserted central catheter line for few weeks as a bridge.

Inclusion criteria for the study included the following:

- Diagnosis of IF, leading to PN dependence based on published guidelines
- Use of heparin locks in preintervention period followed by use of NaHCO₃ locks
- Age <18 years old at time of starting NaHCO₃ locks

Lock solutions

During baseline period, the CVC was flushed with sterile normal saline followed by heparin 10 unit/ml flush syringe. At time of PN initiation, heparin was flushed with sterile normal saline.

During the intervention period, the CVC was flushed with sterile normal saline after PN delivery, followed by placing 8.4% NaHCO₃ lock 0.5–1.5 ml daily (to fill luminal volume determined based on the catheter's priming volume from manufacturer and adjusted per individual patient). This was left to dwell for a minimum of 4 h daily. Before starting PN, the next day, NaHCO₃ locks were aspirated and discarded.

Data collection and outcome measures

A CRBSI was defined as a documented positive blood culture from the CVC in patients showing signs and/or symptoms of infection, including fever, irritability, or hypotension in

the absence of an alternative source of infection. A CRBSI occurring within 1 month of a prior CRBSI with the same organism documented on central blood culture was considered a single CRBSI event. A CRBSI-related CVC replacement event was defined as a replacement procedure because of a documented CRBSI including failed salvage. Event rates were expressed as number of events per 1000 CVC days. Data collected included patient demographics, underlying conditions leading to IF, dates and types of CVC lock use, dates of CRBSI events and CVC placement, and blood culture results.

The primary aim was to compare CRBSI rates between heparin vs NaHCO₃ locks. Both per-protocol analysis, which excluded nonadherent patients, and intent-to-treat (ITT) analysis were conducted and reported for the primary outcome. Secondary outcomes included comparing CVC replacement and repair rates from CRBSIs between groups. The number of catheter days and rates were expressed as medians with interquartile ranges. Event rates were compared using the Wilcoxon signed rank test for paired nonparametric data, with each patient used as their own control, with a significance level set at $P < 0.05$. Statistical analysis was performed using SAS 9.4 (SAS Institute, Cary, NC).

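### The analysis called intent-to-treat has no follow-up window of its own, and the only window given closes when NaHCO₃ locks are discontinued

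*Combined protocol and SAP*

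**What the plan says.** The Study design section sets the calendar limits: "The study covered a period between January 1, 2021, and March 1, 2025". It then divides each patient's time in two. The first part is set out as follows: "Baseline (preintervention) period covered January 1, 2021, until start of NaHCO₃ locks while patients were on heparin locks". The second part opens with the first NaHCO₃ lock and lasts "until the end of the study period or until discontinuation of NaHCO₃ locks, whichever occurred earlier". No third period is defined for time after the locks are stopped.

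The section on data collection and outcome measures states the aim, "The primary aim was to compare CRBSI rates between heparin vs NaHCO₃ locks", and the analysis sets: "Both per-protocol analysis, which excluded nonadherent patients, and intent-to-treat (ITT) analysis were conducted and reported for the primary outcome". It says what per-protocol removes. It does not say which patients, days or events make up the ITT analysis.

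On scale and test: "Event rates were expressed as number of events per 1000 CVC days", and "Event rates were compared using the Wilcoxon signed rank test for paired nonparametric data, with each patient used as their own control". Rates are summarised as medians with interquartile ranges. No pooled rate ratio is planned. The documents give no sample size, event count, number of discontinuations or reasons for stopping.

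**The concern.** A reader who sees ITT reported beside per-protocol takes ITT as the analysis that follows patients whether or not they stay on the intervention. Under the only window in the plan it does not do that. It adds back nonadherent patients who had not stopped, but a patient who stops the locks and keeps the CVC leaves the analysis on that day. Both analyses then share the same truncation, so agreement between them says nothing about its effect.

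This matters if the decision to stop is linked to the outcome. In an open-label study within one programme, stopping after an infection or a lock problem is plausible. The plan neither excludes it nor asks for it to be reported. Follow-up that ends because of an event distorts a per-patient rate, and the per-patient rate is what the planned test compares.

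**Working it through.** **1. Reading the definitions together.** The plan has no figure to reproduce, so the first step is textual.

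| Time in a patient's record | Baseline period | Intervention period |
|---|---|---|
| On heparin, before first NaHCO₃ lock | yes | no |
| On NaHCO₃ locks | no | yes |
| After NaHCO₃ locks stopped, CVC still in use | no | no |

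The third row enters neither numerator nor denominator. No other window is stated, so this applies to both analyses as written.

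**2. Why the planned test is sensitive (hand example).** Suppose a patient has 2 CRBSIs in 800 heparin days: 2/800 × 1000 = 2.5 per 1000 days. After starting NaHCO₃ the patient has one CRBSI on day 100 and none later.
- Full 600 days: 1/600 × 1000 = 1.7, difference 1.7 − 2.5 = −0.8.
- Stopped on day 100: 1/100 × 1000 = 10, difference 10 − 2.5 = +7.5.

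Truncation reverses the sign and gives this patient a large rank.

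**3. Simulation with no true effect.** All inputs are assumptions:
- 25 patients, each with 800 heparin days and 600 post-start days. The total of 1400 fits within the 1520 days of the study period.
- 2.0 CRBSI per 1000 days in every period, so 25 × 800 × 0.002 = 40 heparin events and 25 × 600 × 0.002 = 30 post-start events are expected.
- Patient risk varies by a gamma factor with mean 1 (shape 1 is strong heterogeneity), or does not vary.
- After each on-lock CRBSI the patient stops with probability q. The triggering CRBSI is counted as a NaHCO₃ event.

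Results with gamma shape 1; a range is the spread over repeated runs:

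| q | Post-start CRBSIs dropped | Signed-rank rejection | Pooled rate ratio |
|---|---|---|---|
| 10% | – | 6% | 0.94 |
| 25% | 22–23% | 8–11% | 0.88–0.89 |
| 50% | 38% | 17–20% | 0.79–0.80 |
| 75% | 47% | 27–30% | 0.73–0.74 |

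At q = 75%, 47% of 30 is about 14 expected events lost. With 800 trials, the Monte Carlo standard error near 30% is √(0.30 × 0.70/800) = 1.6 percentage points. With full follow-up, rejection is 4–6% and the pooled ratio about 1.0. From q = 25% upward almost all rejections are against NaHCO₃.

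**4. Dependence on heterogeneity.** The signed-rank distortion persists: at q = 75% it rejects in 32% of trials with shape 2 and 37% with no heterogeneity. The pooled ratio behaves differently:

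| Heterogeneity | q = 25% | q = 50% | q = 75% |
|---|---|---|---|
| Shape 1 | 0.88–0.89 | 0.79–0.80 | 0.73–0.74 |
| Shape 2 | 0.93–0.94 | 0.88–0.90 | 0.84–0.85 |
| Shape 4 | 0.96 | 0.93 | 0.91 |
| None | 1.00 | 0.99 | 1.00 |

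The pooled ratio falls only because high-risk patients stop early and contribute fewer days. With a common rate it stays at about 1.0.

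**5. If the locks do work.** The two windows then answer different questions. With f the share of post-start CVC days after stopping,

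ratio over all post-start days = (1 − f) × RR_on + f × RR_off.

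Assume RR_on = 0.50. With f = 20% and a return to the baseline rate (RR_off = 1.0): 0.8 × 0.50 + 0.2 × 1.0 = 0.60. With RR_off = 1.5: 0.40 + 0.30 = 0.70. At f = 40% the results are 0.70 and 0.90. At f = 0 the windows coincide.

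**The case against.** The strongest reply is that ITT is never defined, so the plan cannot be said to use the truncated window for it. Lock types with their dates and CRBSI dates are listed as collected, and a fuller window may have been used without being written down. This stands as a limit: the documents do not establish that the reported ITT analysis dropped every later event. They do establish that the only window they contain would do so.

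Second, this is a single-group before-and-after cohort selected on having used NaHCO₃ locks. The protection that ITT gives in a randomised trial was never available, and a window closing at discontinuation suits a comparison of one lock with the other. That is fair, and it argues for labelling the window as on-treatment.

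Third, nothing shows that stopping followed infection. If discontinuation meant CVC removal or weaning from PN, no days at risk are lost. This also stands, and is why the size stays conditional.

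A reader might infer that the truncation flatters NaHCO₃, or that the same data could support opposite conclusions. The documents support neither. A ratio below 1 under no effect needs both heterogeneity between patients and a pooled ratio that the plan does not contain. In the same scenarios the planned test errs almost always against NaHCO₃, so for a claim of benefit it is conservative.

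**Conclusion.** The point holds in conditional form. On the text alone, the ITT analysis lacks a window, and applying the only one given makes it on-treatment in follow-up time; it differs from per-protocol only by keeping nonadherent patients.

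The consequence depends on facts not in the documents: how many patients stopped while still having a CVC, why, and what happened afterwards. Under the assumed inputs, false rejection by the planned test runs from about 6% (10% of on-lock CRBSIs leading to stopping) to about 37% (75%, no heterogeneity), against about 5% nominal. Any pooled ratio would lie between about 1.0 and about 0.74. These figures count the triggering CRBSI as a NaHCO₃ event, which the plan does not specify. The effect is small at 10% stopping and zero if stopping coincided with CVC removal or the end of PN. Neither the true size nor the true direction can be determined from the documents.

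**What to change.** 1. Define the ITT analysis as all CVC days and all CRBSIs from the first NaHCO₃ lock to March 1, 2025 or the patient's last CVC day, whatever lock is in use.
2. Keep the present window as a separate analysis labelled on-treatment, and state that a CRBSI leading to discontinuation counts as a NaHCO₃ event.
3. Report the number of patients who discontinued, the reasons, and the CVC days and CRBSIs after stopping.
4. If data after discontinuation cannot be obtained, drop the ITT label and call the analysis on-treatment, all patients. Items 2 and 3 still apply as far as the data allow.

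Cost: a few sentences of plan text and some chart extraction within the same programme. Lock dates and CRBSI dates are already listed as collected, but whether collection continued after discontinuation is not stated. The ITT effect may be diluted if patients returned to their former infection rate after stopping.
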